8.2.3 SENSITIVITY ANALYSIS

Sensitivity analysis will be conducted to compare the different definitions of exposure categories (60 days window vs. 30 day window, 90 day window vs. 30 day window to define recent exposure).

8.2.4 TIME TO EVENT ANALYSIS

Time to event analysis will be conducted as a secondary analysis and the following factors possibly related to incidence of end points will be considered at the date of Incidence or the last visit before incidence: age, BMI, smoking (depending on availability of data), history of diabetes, history of hypertension, history of malignancies, history of VTE, and some other co-morbidities. Univariate Cox models (if applicable, depending on the PH assumptions for each factor, otherwise logistic regression model) will be performed for each factor and then, the analysis will be complemented by a multivariate Cox model (if applicable, depending on the PH assumptions for each factor) or a logistic regression. Hazard ratios (HR) or odds-ratios with 95% CI and p-values will be presented for significant factors at the 0.05 level.

8.2.5 SUMMARY OF STATISTICAL ANALYSIS

Analyses for Primary Objective and Secondary Objective 1

Comparator: BZA vs. bisphosphonate (primary objective), BZA vs. raloxifene (secondary objective 1).

Study endpoint: VTE.

Populations: a. Full BZA full raloxifene, random age stratified bisphosphonate subgroup
b. Incident user subgroup.

Statistical Method:

- i. Incidence rate, cumulative method (*Total new cases during follow-up period / Total persons at risk during follow-up period*) with stratification by risks of interest e.g. Age, BMI.
- ii. Univariate and multivariate incidence rate by incidence density (*Total new cases during follow up period / Total person years during follow-up period*)*1000) method using Cox regression model and a Likelihood Ratio Test for testing Hazard Ratio (HR) =1 (ratio of hazard in BZA population vs. bisphosphonate/raloxifene population) with covariates associated with VTE outcome and exposure (Drug groups).

Sensitivity analyses:

- i. Repeat analysis will be conducted that compares using a 30-day and a 90-day definition of recent exposure with using the 60-day definition.
- ii. Missing Data: First, the analyses will be repeated utilizing a complete dataset in which cases with missing values of main study covariates of BMI, smoking status and alcohol status have been deleted. Second, multiple imputation for the missing values of BMI, smoking status, alcohol status will be used in the second set of analyses.

Multiple imputation procedure:

- 1) Estimate distribution of BMI, smoking status and alcohol status according to patients whose data are available.
- 2) For the patients who had missing values those variables draw values of the variables from the distribution from 1).
- 3) With the imputed dataset (including none-missing data), estimate HR as described.
- 4) Repeat 2)-3) for m times, and record HR of each time.
- 5) Calculate mean of m estimates of HR.
- 6) Adjust variance of HR with the following formula, and use the variance to calculate confidence interval.

$$V = \left(1 + \frac{1}{M}\right) V_B + V_W.$$

V_B is the between imputation variance, and V_W is within imputation variance.

Analyses for Secondary Objective 2 and Secondary Objective 3

Comparator: BZA vs. bisphosphonate (secondary objective 2), BZA vs. raloxifene (secondary objective 3).

Study endpoint: Secondary endpoints.

Population: a. Full BZA, full raloxifene, random age stratified bisphosphonate subgroup.
b. Incident user subgroup

Statistical Method:

- i. Incidence rate, cumulative method (*Total new cases during follow-up period / Total persons at risk during follow-up period*) with stratification by risks of interest e.g. Age, BMI.
- ii. Univariate and multivariate (if covariates available) incidence rate by incidence density (*Total new cases during follow up period / Total person years during follow-up period*)*1000) method using Cox regression model and using a Likelihood Ratio Test for testing Hazard Ratio (HR) =1 (ratio of hazard in BZA population vs. bisphosphonate/raloxifene population) with covariates associated with secondary endpoints and exposure (Drug groups).

Sensitivity analyses:

- i. Repeat analysis will be conducted that compares using a 30-day and a 90-day definition of recent exposure with using the 60-day definition.
- ii. Missing Data: First, the analyses will be repeated utilizing a complete dataset in which cases with missing values of main study covariates of BMI, smoking status and alcohol status have been deleted. Second, multiple imputation for the missing values of BMI, smoking status, alcohol status will be used in the second set of analyses.

Multiple imputation procedure:

- 1) Estimate distribution of BMI, smoking status and alcohol status according to patients whose data are available.
- 2) For the patients who had missing values those variables draw values of the variables from the distribution from 1).
- 3) With the imputed dataset (including none-missing data), estimate HR as described.
- 4) Repeat 2)-3) for m times, and record HR of each time.
- 5) Calculate mean of m estimates of HR.
- 6) Adjust variance of HR with the following formula, and use the variance to calculate confidence interval.

$$V = \left(1 + \frac{1}{M}\right) V_B + V_W.$$

V_B is the between imputation variance, and V_W is within imputation variance.

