7 HANDLING OF MISSING VALUES

For each variable, the number and proportion of patients missing data for each treatment group will be specified. The primary analyses will be done using only the information available in the unmodified dataset. Smoking status, alcohol consumption, height and/or weight (BMI) values are known to be missing for approximately 40-60% patients in the Cegedim LPD based on previous studies. (Age of patients will always be known as it is a selection criterion). Dates are automatically recorded in the Cegedim LPD and doctors can select diseases codes from the pre-defined lists. In all analyses, if a condition (disease or treatment) other than the diagnosis of osteoporosis is not recorded, it will be assumed to be non-existent.

To estimate the effect of missing data, two additional analyses for the primary study endpoint will be conducted. First, the analyses will be repeated utilizing a dataset in which cases with missing values of main study covariates of BMI, smoking status and alcohol status are excluded. The disadvantage to this approach is the reduction in the sample size. Another disadvantage to this approach is that the subjects with missing values may be different than the subjects without missing values (e.g., missing values that are not missing at random), resulting in a non-representative sample after removing the cases with missing values. Second, multiple imputations for the missing values of BMI, smoking status, alcohol status will be used in the second set of analyses and compared to complete case analyses to understand the potential impact of missing data on results [2].

Outlier

Extreme values for weight and height will be searched for. If a value seems implausible, as regard to gender or ratio weight/height, it will be put as missing.

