Venous Thromboembolic Events (VTE) are defined as deep vein thrombosis, pulmonary embolism, retinal vein thrombosis, and venous sinus thrombosis. This objective is to compare this incidence in real life settings with validated diagnosis codes, ICD9 in Italy and International Classification of Primary Care (ICPC) codes in Spain.

The availability of medical history of all relevant medical diagnosis for patients will be checked in both the Spanish and the Italian database and presented if available. The variables of medical history (diabetes, hypertension, VTE and Malignancies) will be presented in classes (Yes/No) before index date. (All the detailed diagnosis codes of each endpoint have been validated by Pfizer and are available in a separate reference document). For all medical history and smoking status, if the relevant information is not found in the database, it will be assumed to be negative.

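### As literally written, the SAP's multiple imputation ignores treatment and outcome, so it retains most of the confounding from an imputed covariate; pooling on the HR scale would also shift both confidence limits down

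*SAP*

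**What the plan says.** SAP 8.2.5 sets out a six-step procedure, once for VTE and again for the secondary endpoints. Step 1: "Estimate distribution of BMI, smoking status and alcohol status according to patients whose data are available". Step 2: "For the patients who had missing values those variables draw values of the variables from the distribution from 1". Treatment, event, follow-up time, age and country are not mentioned. Step 5: "Calculate mean of m estimates of HR". Step 6: "Adjust variance of HR with the following formula, and use the variance to calculate confidence interval", using the usual sum of within- and between-imputation variance. No log transformation and no number of imputations are given.

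SAP 7 expects a lot of missing data: BMI, smoking and alcohol "values are known to be missing for approximately 40-60% patients in the Cegedim LPD", a figure taken from previous studies. It makes the imputation an additional analysis, to be "compared to complete case analyses to understand the potential impact of missing data on results", and introduces it for the primary study endpoint only. The main result does not use it: "The primary analyses will be done using only the information available in the unmodified dataset".

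SAP 8.1.1 has a competing rule for smoking: "For all medical history and smoking status, if the relevant information is not found in the database, it will be assumed to be negative".

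On covariates, SAP 8.1.4 lists BMI and smoking among the Cox factors, lets smoking be dropped if rarely recorded, and admits variables with univariate p of 0.20 or less. Alcohol appears in neither Cox factor list (8.1.4, 8.2.4). SAP 8.2.4 calls the time-to-event analysis secondary, although 4.2 and 8.2.2 use the Cox HR to compare event rates.

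**The concern.** A value drawn without regard to treatment or outcome carries no information about either. Mixing such values with real ones shrinks the covariate's difference between drug groups and weakens its association with the endpoint. Adjustment then removes only part of the confounding, and the imputed HR moves towards the HR not adjusted for that variable. This happens even under missing completely at random, where the complete-case estimate is valid. The check would then carry a bias of its own making, although its purpose is to show the effect of missing data. The weakened association may also fail the p-value screen, which would leave all of that variable's confounding in place.

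The pooling scale is a separate matter. In a safety study the upper confidence limit shows what excess risk can be excluded. A symmetric interval on the HR scale puts that limit too low.

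**Working it through.** **1. The plan's own figures.** SAP 5.4: 1,823 × 6 = 10,938 bisphosphonate women, which reproduces. For Protocol Table 3, use 1.74/1000 PY and the log-scale Wald interval IRR × exp(±1.96s), with s = √(1/e1 + 1/e0), where e1 and e0 are the expected events. Person-years per woman are not stated. Taking 5 × 0.85 = 4.25 reproduces 22 of 24 limits, including the whole 1:6 row (1,750 vs 10,500):

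| IRR | Printed | Log scale | Symmetric HR scale |
|---|---|---|---|
| 1 | 0.6, 1.8 | 0.56, 1.80 | 0.41, 1.59 |
| 1.5 | 0.9, 2.5 | 0.91, 2.47 | 0.75, 2.25 |
| 2 | 1.3, 3.1 | 1.28, 3.12 | 1.11, 2.89 |

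So the protocol's precision figures follow the log scale. Compounding the 15% loss every year (3.42 PY) matches only 3 of 24 limits.

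**2. Share of confounding retained.** If a fraction f is missing, the group difference and the covariate effect each shrink by roughly (1−f). The share retained is therefore about 1 − (1−f)²: 64%, 75% and 84% at 40, 50 and 60% missing.

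Worked case (assumed): a binary covariate with prevalence 15% in BZA and 35% in bisphosphonate, RR 2, true drug HR 1.
- Unadjusted HR = (1 + 0.15)/(1 + 0.35) = 0.852.
- Overall prevalence = (1,823 × 0.15 + 10,938 × 0.35)/12,761 = 32.1%.
- After literal draws at 40% missing: BZA 0.6 × 15 + 0.4 × 32.1 = 21.9%; bisphosphonate 0.6 × 35 + 0.4 × 32.1 = 33.9%. The gap falls from 20 to 12 points, and the fitted covariate RR from 2 to 1.52.
- Poisson regression on the expected cells gives HR 0.900. Share retained = ln 0.900/ln 0.852 = 66%.

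The same calculation for four assumed settings (complete-case HR is 1.00 in each):

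| Prevalence BZA vs bisphosphonate, RR | Unadjusted HR | Literal MI, 40% to 60% missing | Retained |
|---|---|---|---|
| 15% vs 35%, 2 | 0.852 | 0.900 to 0.872 | 66-85% |
| 35% vs 15%, 2 | 1.174 | 1.107 to 1.144 | 64-84% |
| 20% vs 30%, 1.5 | 0.957 | 0.972 to 0.963 | 64-84% |
| 20% vs 25%, 1.5 | 0.978 | 0.986 to 0.981 | 64-84% |

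With equal prevalence or RR 1, literal MI gives 1.000. Imputing by treatment and event gives 1.000 in all four settings.

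A version with four BMI groups plus age used the bisphosphonate ages in SAP 5.4 and assumed values elsewhere (BZA women younger and leaner, higher risk with higher BMI). The HR adjusted for age only is 0.901, literal MI 0.934 to 0.916, complete case 1.000. Adjustment for recorded age survives; the BMI part mostly does not.

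**3. Pull against noise.** In simulations of these four binary settings at 1,823 vs 10,938, the pull on log HR averaged 0.10-0.14 (strong) or 0.015-0.038 (mild). The SD of the complete-case minus MI gap was 0.23-0.44.

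**4. Pooling scale.** At 4.25 PY and IRR 1: e1 = 1,823 × 4.25 × 0.00174 = 13.5, e0 = 80.9, s = 0.294. At IRR 2: e1 = 27.0, s = 0.222. The symmetric limits are IRR × (1 ± 1.96s). Both lie below the log-scale limits because exp(x) exceeds 1 + x for any non-zero x.

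| IRR | Symmetric HR scale | Log scale | Upper limit below truth (HR vs log) | Total non-coverage (HR vs log) |
|---|---|---|---|---|
| 1 | 0.42-1.58 | 0.56-1.78 | 6.2% vs 1.6% | 6.8% vs 4.5% |
| 2 | 1.13-2.87 | 1.29-3.09 | 5.1% vs 2.0% | 5.8% vs 4.7% |

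The percentages are exact sums over two Poisson counts, without between-imputation variance. At 3.42 PY the upper-limit error on the HR scale is 6.5% (IRR 1) and 5.4% (IRR 2), with total non-coverage 7.0% and 6.0%. Averaging HRs instead of log HRs moves the point estimate by only 0.02-0.5%, for an assumed between-imputation SD of 0.02-0.10.

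**The case against.** **The text is a summary.** Section 8.2.5 is headed as one, and SAP 7 cites a reference for the imputation that was not available here. Conditional imputation may have been intended, and variance of the HR may be loose wording for that of the log HR. Step 6 never writes out a symmetric interval. This stands as a limit on certainty: both effects hold for the literal reading. But a programmer following the six steps would have no instruction to do otherwise.

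**The effect may be small.** No document gives a covariate prevalence or effect, and the 40-60% comes from earlier studies. Alcohol is in no Cox list, smoking may be dropped, and BMI must pass the screen, so BMI may be the main route. This stands for the absolute bias. The share retained hardly depends on these inputs.

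**The check is weak anyway.** For VTE, the noise comes mainly from deleting women with a rare endpoint. The full-data SE of log HR is about 0.29; for complete cases it is 0.29/√0.6 = 0.38 or 0.29/√0.4 = 0.46. Even perfect recovery of every missing value would leave a gap SD of about √(0.38² − 0.29²) = 0.24 up to 0.36. This stands: the fix removes a bias and does not create precision.

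**Stronger readings to avoid.** A reader might infer that the study's main estimate is biased. SAP 7 keeps the primary analyses on the unmodified dataset, so it is not affected by this step. A reader might also infer that interval coverage collapses, but total non-coverage rises only to about 6-7%. Nor does the upper limit alone move; the lower limit falls too, and at IRR 2 both versions still exclude 1.

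**Conclusion.** The point holds for the procedure as literally written. If an imputed variable differs between drug groups, predicts the endpoint and stays in the Cox model, the imputed HR retains about 64-85% of that variable's confounding at 40-60% missing, even under missing completely at random. The resulting bias is about 1-4% under the mild and 10-14% under the strong assumptions, and nil if the variable is balanced or not prognostic.

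If steps 5-6 are applied as a symmetric HR-scale interval, the whole interval shifts down, and the upper limit falls below the true IRR in about 5-6.5% of studies against a nominal 2.5%.

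Two inconsistencies stand whatever the reading. Smoking that is not recorded is negative in 8.1.1 but missing in 7 and 8.2.5. Imputation is limited to the primary endpoint in 7 but repeated for secondary endpoints in 8.2.5.

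This is a defect in a sensitivity analysis. It deserves correction because the stated steps give a systematically wrong answer and a better method is readily available.

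**What to change.** - Replace steps 1-2, in both places, with a conditional imputation model (chained equations or a joint model). Include treatment group, event indicator, cumulative hazard or follow-up time, age and the baseline Cox covariates.
- Leave out covariates defined only by the month before a VTE unless they are also defined for women without one.
- Fit the model in the pooled data with country as a covariate, and in Spain. Do not rely on a separate full model for Italy: about 40 patients × 4.25 PY × 0.00174 gives about 0.3 expected VTEs.
- Pool log HRs and their variances with the formula already given, then exponentiate the estimate and limits.
- Reconcile 8.1.1 with 7 and 8.2.5 on unrecorded smoking, and 7 with 8.2.5 on which endpoints are imputed. If secondary endpoints are kept, use each endpoint's own event indicator.

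No new data are needed. The cost is SAP wording, some extra programming (more if each secondary endpoint has its own model), and a slightly higher upper confidence limit. Conditional imputation does not cure missingness that depends on the unseen value itself.

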9 LIST OF TABLES AND TABLE SHELLS

Not Applicable

